### 10.2.1 Discontinuation of Study Therapy after CR

Discontinuation of treatment may be considered for subjects who have attained a confirmed CR that have been treated for at least 24 weeks with pembrolizumab and had at least two treatments with pembrolizumab beyond the date when the initial CR was declared. Subjects

who then experience radiographic disease progression may be eligible for up to one year of additional treatment with pembrolizumab via the Second Course Phase at the discretion of the investigator if no cancer treatment was administered since the last dose of pembrolizumab, the subject meets the safety parameters listed in the Inclusion/Exclusion criteria, and the trial is open. Subjects will resume therapy at the same dose and schedule at the time of initial discontinuation.

### **10.3 Clinical Criteria for Early Trial Termination**

Early trial termination will be the result of the criteria specified below:

1. Quality or quantity of data recording is inaccurate or incomplete
2. Poor adherence to protocol and regulatory requirements
3. Incidence or severity of adverse drug reaction in this or other studies indicates a potential health hazard to subjects
4. Plans to modify or discontinue the development of the study drug

In the event of Merck decision to no longer supply study drug, ample notification will be provided so that appropriate adjustments to subject treatment can be made.

## **11.0 DELIVERY OF RADIATION THERAPY TREATMENT**

Definitive SRS will be administered for up to 1-10 lesions using stereotactic radiosurgery techniques starting on day 2-3. Treatment will be timed such that the first fraction of radiation will be delivered 24-48 hours after the first infusion of pembrolizumab. SRS will consist of 1-5 treatments, depending on dose level. For multiple fraction regimens, each treatment will be delivered > 40 hours apart, and should be completed by week 2, day 14.

### **11.1.2 Radiation Simulation and Diagnostic Procedures**

1. All simulation and treatment procedures represent current institutional practice and will be the same for all study participants in each dose level

**CT Simulation:** A CT simulation will be performed for radiation therapy treatment planning purposes several days to the initiation of radiation therapy. This procedure consists of a CT scan performed in the treatment position. It is not for diagnostic purposes and is not itself therapeutic, but the CT image is required for radiation planning and delivery. This procedure is standard of care prior to therapeutic radiation. The CT simulation will occur with the patient supine position in a framed and/or frameless thermoplastic head mask at discretion of treating physician.

-CT simulation scan slice thickness may not exceed 1.25 mm

2. **Pre-treatment MRI of the brain:** A high resolution MRI with and without gadolinium contrast for treatment planning will be acquired within 2 weeks before treatment delivery. This planning MRI is standard of care for patients with intracranial metastases planned for SRS.

-Treatment planning MRI slice thickness may not exceed 3 mm.

### **11.1.3 SRS Based Radiation Therapy Options Criteria**

1. Treatment shall be delivered with one of two approaches:
  - a. Linear accelerated (LINAC) based stereotactic radiosurgery
  - b. Gamma knife based stereotactic radiosurgery

### **11.1.4 LINAC, SRS Based Radiation Therapy, Required Criteria**

1. Treatment shall be delivered with megavoltage machines of a minimum energy of 4 MV photons. Selection of the appropriate photon energy should be based on optimizing the radiation dose distribution within the target volume and minimizing dose to non-target normal tissue.
2. LINAC treatment should also include isocentric conical collimators, mini-multi-leaf (5 mm or less) technology or linear accelerators mounted on robotic arms.
3. Either a framed or frameless stereotactic, relocatable immobilization system will be used for treatment simulation and delivery. These systems may include modified stereotactic frames, camera-based localization systems, etc. The immobilization/ relocalization system should be capable of reproducing the patient setup to within 3 mm.
4. Single fraction radiosurgery treatment may be delivered with intensity modulated radiation surgery (IMRS) or dynamic conformal arcs (DCA). Multiple fraction radiation treatment can be delivered by intensity modulated radiation therapy (IMRT) or volume modulated arc therapy (VMAT).
5. Patients must be positioned for each treatment using 3-dimensional imaging i.e.  
**Cone Beam CT.** Cone beam CT scans with each radiation fraction on the treatment machine will be performed daily prior to SRS with the patient in the treatment position to assure accurate repositioning of the PTVs.
6. Radiation therapy will consist of 1-5 fractions. All radiation treatment fractions should be completed by end of week 2 of treatment
7. Multiple vertex and coplanar/noncoplanar beams should be used and arranged with the goal of excluding as much normal brain tissue as possible outside of the PTV at high and intermediate dose levels.

### **11.1.5 Gamma Knife, SRS Based Radiation Therapy, Required Criteria**

1. Treatment shall be delivered with megavoltage machines of a minimum energy of 4 MV photons. Selection of the appropriate photon energy should be based on optimizing the radiation dose distribution within the target volume and minimizing dose to non-target normal tissue.
2. Single fraction radiosurgery treatment may be delivered with intensity modulated radiation surgery (IMRS) or dynamic conformal arcs (DCA). Multiple fraction radiation treatment can

be delivered by intensity modulated radiation therapy (IMRT) or volume modulated arc therapy (VMAT).

3. Patients must be positioned for each treatment using 3-dimensional imaging i.e. Cone Beam CT.

Cone beam CT scans with each radiation fraction on the treatment machine will be performed daily prior to SRS with the patient in the treatment position to assure accurate repositioning of the PTVs.

4. Radiation therapy will consist of 1-5 fractions. All radiation treatment fractions should be completed before end of week 2 of treatment.

#### **11.1.6 Target Volume Determination**

1. The gross tumor volume (GTV) will be defined by as the MRI defined T1 post contrast enhancing brain metastasis. Surrounding areas of edema will not be considered part of the target volume

2. The clinical target volume (CTV) will be the GTV without margin in all directions

-for resected brain metastases, an 1mm expansion should be utilized:  
 $CTV_{\text{resection-cavity}} = GTV_{\text{resection-cavity}} + 1\text{mm expansion.}$

3. The planning target volume (PTV) will be the CTV + 1.5 mm margins.

#### **11.1.7 Total dose determination**

All three arms will initially enroll patients, followed by a 3 month toxicity assessment for dose limiting toxicity (i.e. radionecrosis); If clinically significant necrosis (as defined in section

2.0) is noted, this arm will be stopped. However, enrollment on the other arms will continue.

#### **11.1.8 Dose prescription and dosimetry requirements**

1. Dose will be prescribed to the isodose line that encompasses the entirety of the PTV. Treatment planning and dose acceptance will be per institutional standard of care.

A. If intensity modulated radiosurgery (IMRS) is utilized, standard prescription isodose is to 98% (range 95-100%, acceptable)

B. If dynamic conformal arcs (DCA) are utilized, standard prescription isodose is to 80% (range 70-90%, acceptable).

C. If gamma knife is used, standard prescription isodose is to 50% (range 40-60% acceptable)

2. Doses are specified such that at least 95% of the PTV shall receive 100% of the prescribed dose.

3. The marginal dose and the 100% dose (isocenter dose) may be recorded for each patient.

4. For quality control, representative isodose lines (e.g. 20%, 40%, 60%, 80%, 90%) may be generated for each patient.

Quality of PTV coverage will be categorized according to selected isodose line:

- A. Total – selected isodose line completely encompasses the PTV
- B. Marginal – selected isodose line incompletely encompasses the PTV, but not by more than 10% of the PTV volume.
- C. Subtotal - selected isodose line incompletely encompasses the PTV, but by more than 10% of the PTV volume. This will not be accepted.

5. Conformality index requirements (ratio of prescription isodose volume to the target volume ( $PI/TV$ ))

- 1. Per protocol if between 1.0 and 2.0, acceptable
- 2. Acceptable variation if  $\geq 0.9$  but  $< 1.0$  or  $> 2.0$  but  $\leq 3.5$ .
- 3. Unacceptable deviation if  $> 3.5$ .

**11.1.9 Dose Limitation to Critical Structures**

1. In addition to the above defined GTVs, CTVs and PTVs, both eyes, the lenses of both eyes, the optic nerves, the optic chiasm, cochlea, the brainstem, and the spinal must be evaluated per standard of care approaches. Dose-volume histograms will be generated and whole organ dose and maximum point dose will be recorded for each critical structure. Dose limitations to normal structures are defined in **Table 9**.

2. If the patient has received no prior cranial irradiation, the maximal point doses permissible to the structures from the current radiation therapy plan are listed below.

3. Patient cannot have received whole brain radiation or SRS prior to being enrolled on this trial. However, once on the trial, patient can have received multiple SRS and or whole brain radiation as part of the standard of care treatments for progressive disease; If the patient has received previous brain radiation therapy (while on the trial), the previous dose received to critical structures should be obtained or a representative dose distribution file should be simulated. This dose should then be converted to BED (assuming an alpha-beta ratio of 3 for late effects) and added to the BED to the critical structures from the current treatment plan. This sum BED must meet the cumulative dose constraint below. No adjustments for time between previous radiation treatment will be made for the purpose of this protocol.

**Table 9 – Normal Tissue Constraints Based on the number of radiation fractions**

Normal Tissue Constraints, 5 Radiation Fractions					
Cumulative BED 3	Volume		No Previous RT*	Previous RT 	Endpoint ( $\geq$ Grade 3 AE)
			Maximum Dose (Gy)	Maximum Cumulative BED 3	
Brainstem	Max,	$\leq$	26	90	Cranial Neuropathies
	0.03cc				

Spinal Cord	Max, 0.03cc	≤	22.5	75	Myelitis
Eye (Globe), each	Max, 0.03cc	≤	20	66	Vision Loss
Lens, each	Max, 0.03cc	≤	5	12	N/A*
Optic Nerve, each	Max, 0.03cc	≤	25	90	Vision Loss
Optic Chiasm	Max, 0.03cc	≤	25	90	Vision Loss
Cochlea	Max, 0.03cc	≤	27.5	90	Hearing Loss

Normal Tissue Constraints, 3 Radiation Fractions

Cumulative BED 3	Volume		No Previous RT*	Previous RT †	Endpoint (≥ Grade 3 AE)
			Maximum Dose (Gy)	Maximum Cumulative BED 3	
Brainstem	Max, 0.03cc	≤	18	90	Cranial Neuropathies
Spinal Cord	Max, 0.03cc	≤	18	75	Myelitis
Eye (Globe), each	Max, 0.03cc	≤	18	66	Vision Loss
Lens, each	Max, 0.03cc	≤	4	12	N/A*
Optic Nerve, each	Max, 0.03cc	≤	15	90	Vision Loss
Optic Chiasm	Max, 0.03cc	≤	15	90	Vision Loss
Cochlea	Max, 0.03cc	≤	20	90	Hearing Loss

Normal Tissue Constraints, 1 Radiation Fraction

Cumulative BED 3	Volume		No Previous RT*	Previous RT †	Endpoint (≥ Grade 3 AE)
			Maximum Dose (Gy)	Maximum Cumulative BED 3	

Brainstem	Max, 0.03cc	≤	10	90	Cranial Neuropathies
Spinal Cord	Max, 0.03cc	≤	18	75	Myelitis
Eye (Globe), each	Max, 0.03cc	≤	16	66	Vision Loss
Lens, each	Max, 0.03cc	≤	2.5	12	N/A*
Optic Nerve, each	Max, 0.03cc	≤	8	90	Vision Loss
Optic Chiasm	Max, 0.03cc	≤	8	90	Vision Loss
Cochlea	Max, 0.03cc	≤	12	90	Hearing Loss

\*Lens toxicity is cataract formation, which for the purposes of this trial is not a dose limiting toxicity.

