#### 11.1.11 Progression of CNS disease

If a patient has new CNS lesions on the 6 weeks follow-up MRI, patient can undergo repeat SRS to the new lesions and/or whole brain radiation treatments (and/or CSI-if leptomeningeal disease), at the discretion of the treating physician, and per routine standard of care. However, if there is any doubt, please contact the PI. The goal is to continue to manage the patient per routine standard of care to salvage the intra-cranial disease by either repeated SRS treatments to the new lesions and/or whole brain radiation treatments (Cranio-spinal XRT can be used if significant leptomeningeal disease is suspected). The patient would still continue with anti-PD-1 treatments until progression of extra-cranial disease, undue toxicity, and/or at least 2 year, at the discretion of the treating physician. Radiation treatments should be timed with the administration of the next cycle of PD-1 treatments, or as close as possible (whenever clinically possible/applicable);

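### Table 9's single-fraction limits for spinal cord (18 Gy) and globe (16 Gy) exceed those rows' own cumulative BED3 ceilings, at 168% and 154%, so a permitted first course can leave the re-irradiation rule impossible to meet

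*Combined protocol and SAP*

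**What the plan says.** Section 11.1.9 applies two limits in two situations.

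- **First course.** The Gy column of Table 9 applies here: "If the patient has received no prior cranial irradiation, the maximal point doses permissible to the structures" are those listed in the table.
- **Re-irradiation.** The second limit begins "If the patient has received previous brain radiation therapy (while on the trial"). The earlier dose to each structure is obtained or simulated, and then: "This dose should then be converted to BED (assuming an alpha-beta ratio of 3 for late effects"). It is added to the BED of the current plan, and "This sum BED must meet the cumulative dose constraint below". Recovery is not credited: "No adjustments for time between previous radiation treatment will be made for the purpose of this protocol".

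Table 9 has three blocks, for five, three and one fractions, with seven structures in each. In the block "Normal Tissue Constraints, 1 Radiation Fraction", the cord row allows 18 Gy with a cumulative BED3 ceiling of 75 and lists myelitis as the endpoint. The globe row allows 16 Gy with a ceiling of 66 and lists vision loss.

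Section 11.1.11 expects re-irradiation. With new CNS lesions, a "patient can undergo repeat SRS to the new lesions and/or whole brain radiation treatments", and "Cranio-spinal XRT can be used if significant leptomeningeal disease is suspected". Arm C is the single-fraction arm (Table 1), and Section 14.2 continues its enrolment to 12 patients.

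**The concern.** The re-irradiation rule counts the first course in the sum. Because BED only accumulates, a ceiling below the permitted first-course dose cannot be met by any later plan, however small its dose. That differs from a strict re-irradiation limit, which would still leave some room.

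For these two structures the columns also cannot both describe one tolerance. A patient with a trivial earlier dose would be held to roughly 13.5 Gy (cord) or 12.6 Gy (globe) in one fraction, while a patient with none may receive 18 or 16 Gy.

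At stake is a safety threshold. If the Gy entries are wrong, the table permits first-course doses well above the BED3 that the protocol accepts cumulatively. If the ceilings are wrong, it blocks salvage treatment that the protocol allows elsewhere.

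**Working it through.** **Inputs.** Alpha/beta of 3, the summation rule and the absence of a time adjustment come from Section 11.1.9. Dose limits and ceilings come from Table 9.

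**Formula.** BED = D × (1 + (D/n)/(alpha/beta)), with D the total dose and n the number of fractions.

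**Check against the plan's own figures.** With alpha/beta 3, the chronic BEDs in Table 1 are:

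- 6 Gy × 5: 30 × (1 + 6/3) = 90 (printed 90)
- 9 Gy × 3: 27 × (1 + 9/3) = 108 (printed 108)
- 21 Gy × 1: 21 × (1 + 21/3) = 168 (printed 168)
- 18 Gy × 1: 18 × (1 + 18/3) = 126 (printed 128, a separate slip of 2 units that does not affect this point)

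The formula is therefore the one the protocol uses.

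**The two rows.**

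- Cord, one fraction: 18 × (1 + 18/3) = 126.0. 126.0/75 = 168%, an excess of 51.0 units.
- Globe, one fraction: 16 × (1 + 16/3) = 101.3. 101.3/66 = 154%, an excess of 35.3 units.

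**All 21 rows**, as Gy → BED3 (share of ceiling):

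| Structure | Ceiling | 1 fraction | 3 fractions | 5 fractions |
|---|---|---|---|---|
| Brainstem | 90 | 10 → 43.3 (48%) | 18 → 54.0 (60%) | 26 → 71.1 (79%) |
| Spinal cord | 75 | **18 → 126.0 (168%)** | 18 → 54.0 (72%) | 22.5 → 56.3 (75%) |
| Globe | 66 | **16 → 101.3 (154%)** | 18 → 54.0 (82%) | 20 → 46.7 (71%) |
| Lens | 12 | 2.5 → 4.6 (38%) | 4 → 5.8 (48%) | 5 → 6.7 (56%) |
| Optic nerve | 90 | 8 → 29.3 (33%) | 15 → 40.0 (44%) | 25 → 66.7 (74%) |
| Optic chiasm | 90 | 8 → 29.3 (33%) | 15 → 40.0 (44%) | 25 → 66.7 (74%) |
| Cochlea | 90 | 12 → 60.0 (67%) | 20 → 64.4 (72%) | 27.5 → 77.9 (87%) |

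The 19 sound rows leave 13% to 67% of the ceiling for re-irradiation.

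**Internal pattern.** Three comparisons within the table point to the same two entries.

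- For the other five structures, the single-fraction limit has the lowest BED3 of the three schedules. For cord and globe it has the highest, by about a factor of two.
- The cord limit is 18 Gy in both the one- and three-fraction blocks, although the same total converts to 126.0 in one fraction and 54.0 in three.
- The ceilings rank cord (75) below brainstem (90) and globe (66) below optic nerve (90). The five-fraction Gy limits keep that order (22.5 against 26, 20 against 25). The single-fraction limits reverse it (18 against 10, 16 against 8).

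**Break-even dose.** Setting D + D²/3 = C gives D = 1.5 × (√(1 + 4C/3) − 1).

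- Cord, C = 75: D = 13.57 Gy
- Globe, C = 66: D = 12.65 Gy

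A permitted single-fraction dose between 13.57 and 18 Gy to the cord, or between 12.65 and 16 Gy to a globe, is already over the cumulative ceiling.

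**The case against.** The arithmetic is not in dispute, and nothing elsewhere in the protocol corrects the two rows. The case on the other side concerns consequence and remedy.

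- **Unseen footnote.** The Previous RT column carries a note marker whose text is not visible in the extracted document, and it might qualify the ceiling. This is a fair caution, but the body of Section 11.1.9 states the sum rule in full.
- **Rarity.** Brainstem metastases are excluded. In the same block the brainstem is capped at 10 Gy, each optic nerve at 8 Gy and each lens at 2.5 Gy. A compliant plan with more than 13.57 Gy to the cord or 12.65 Gy to a globe would need unusual geometry, followed by re-irradiation. This stands as a limit on how often the problem arises.
- **Other safeguards.** Plan acceptance follows institutional standard of care, and salvage is at the physician's discretion. These reduce the practical risk, but they do not repair a mandatory rule that a compliant first course already breaks.
- **Other rows can also block salvage.** No whole-brain dose is given, so this needs an assumption. If a structure at its first-course limit then received the full whole-brain dose, 30 Gy in 10 fractions (BED3 60.0) would breach the ceiling in 10 of the 12 brainstem, optic nerve, chiasm and cochlea rows. With 20 Gy in 5 fractions (46.7), it would in 7 of 12. This narrows the point: what is peculiar to cord and globe is that the ceiling is exceeded before any second dose is given.
- **Remedy.** The documents do not show which column is wrong, and lowering the Gy entries to break-even leaves almost nothing for re-treatment. Both are true, and the fix allows for them.

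**Conclusion.** The concern holds. Under the protocol's own conversion, two of the 21 rows in Table 9 permit a first-course dose above their cumulative ceiling: single-fraction cord at 168% and single-fraction globe at 154%. After such a course the re-irradiation rule cannot be satisfied for that structure.

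The result rests only on the alpha/beta of 3, the summation rule and the absence of a time adjustment, all set in Section 11.1.9. It is confined to single-fraction courses that put more than 13.57 Gy on the cord or 12.65 Gy on a globe. The documents do not give the frequency of such plans, and no effect on the 3-month DLT endpoint is claimed. It should be corrected because it is a wrong safety threshold for structures whose listed endpoints are myelitis and vision loss, and the correction is simple.

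**What to change.** The radiation team should decide which column is wrong for the two single-fraction rows and amend Table 9.

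- **If the ceilings of 75 and 66 stand,** reduce the limits to at most about 13.5 Gy for cord (BED3 74.25) and 12.6 Gy for globe (BED3 65.5). These are upper bounds. Lower values are needed if usable room for re-irradiation is wanted.
- **If the Gy limits stand,** correct and justify the ceilings.

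The same amendment should recheck all 21 rows against the BED3 rule and confirm the text of the note to the Previous RT column. The cost is a table correction in an amendment, with no added patients, visits or procedures.

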#### 11.1.10 Radiation Toxicity Evaluation

Patients should undergo evaluation for development of acute and chronic radiotherapy toxicity at the time of protocol visits. This should be done 1 month after completing SRS (between weeks 4-6 post SRS, per standard of care) and then during follow-up visits and maintenance therapy every 3 months, or as otherwise indicated. Suspected radiosurgery-related toxicity should be graded using the CTCAE 4.0 adverse events grading system. If there is a suspicion of a novel or unexpected toxicity of grade 3 or higher severity that is suspected to be related to the combination of pembrolizumab and radiosurgery, the study coordinator should be immediately notified. If possible, a determination should be made whether the toxicity is likely to be the result of immune therapy, radiosurgery or was exacerbated by the combination. The AE or SAE should be attributed as definite, probable, possible, or unlikely for each.

#### 11.1.11 Progression of CNS disease

If a patient has new CNS lesions on the 6 weeks follow-up MRI, patient can undergo repeat SRS to the new lesions and/or whole brain radiation treatments (and/or CSI-if leptomeningeal disease), at the discretion of the treating physician, and per routine standard of care. However, if there is any doubt, please contact the PI. The goal is to continue to manage the patient per routine standard of care to salvage the intra-cranial disease by either repeated SRS treatments to the new lesions and/or whole brain radiation treatments (Cranio-spinal XRT can be used if significant leptomeningeal disease is suspected). The patient would still continue with anti-PD-1 treatments until progression of extra-cranial disease, undue toxicity, and/or at least 2 year, at the discretion of the treating physician. Radiation treatments should be timed with the administration of the next cycle of PD-1 treatments, or as close as possible (whenever clinically possible/applicable);

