## 2.0 TRIAL DESIGN/SCHEMA

### 2.1 Trial Overview

Pembrolizumab (i.e. anti-PD-1) and stereotactic radiosurgery (SRS) will be delivered concurrently. The safety and efficacy of this combination is not known. Preclinical data shows promise of this combination, but, has yet to be tested in humans with brain metastases. Pembrolizumab (**200 mg IV every 3 weeks +/- 7 days for at least 2 years, or until progression**) will be delivered on day 1 of cycle 1 and continued until at least 2 years or until disease progression per RECIST 1.1 (see Appendix II for RECIST Criteria). SRS will be delivered on day 2 or day 3 of cycle 1 (i.e. within 24-48 hours after anti-PD-1, with some flexibility allowed for SRS timing during cycle 1).

Three different radiation doses (**Table 1**) will be delivered during cycle 1, in combination with Pembrolizumab. All three radiation doses have different biological effectiveness doses (BED) for acute and late side effects, with Arm C being the most commonly used accepted arm; The **primary objective** will be to assess for dose limiting toxicity (i.e.  **$\geq$  grade 3 CNS toxicity at 3 months**) when different radiation doses (**Table 1**) are delivered; Several secondary objectives will also be evaluated (**section 3.0**); The primary point of the trial (dose limiting toxicity) is  $\geq$  radiation therapy oncology (RTOG) CNS grade 3 toxicity, as defined in the original RTOG 90-05 trial, used to arrive at the currently used safest single radiation dose fraction (**Arm C, Table 1**) schemes for radiosurgery (Shaw E, et al. Int. J. Rad. Onc. & Biol. 2000(47) 291-8); **Grade 3 CNS toxicity is defined as irreversible severe neurological symptoms as outpatient or inpatient requiring medication usage**; It is also possible that while changing the radiation dose levels, we may also find a radiation dose level that is also more immunogenic when combined with PD1 inhibitor; This optimal radiation dose may or may not be the same as that per RTOG 90-05; Preclinical data suggest that dose fraction sizes of 8-10 Gy may be more immunogenic compared with other dose fractionation regimens; This needs to be further evaluated in clinical trials;

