## 10.2 Subject Withdrawal/Discontinuation Criteria

Subjects may withdraw consent at any time for any reason or be dropped from the trial at the discretion of the investigator should any untoward effect occur. In addition, a subject may be withdrawn by the sponsor-investigator if enrollment into the trial is inappropriate, the trial plan is violated, or for administrative and/or other safety reasons

A subject must be discontinued from the trial for any of the following reasons:

- The subject or legal representative (such as a parent or legal guardian) withdraws consent.
- Confirmed extra-cranial radiographic disease progression
- Unacceptable adverse experiences as described in section 7, 8, and 9.
- Intercurrent illness that prevents further administration of treatment
- Investigator's decision to withdraw the subject
- The subject has a confirmed positive serum pregnancy test
- Noncompliance with trial treatment or procedure requirements
- The subject is lost to follow-up
- Completed at least 24 months of uninterrupted treatment with pembrolizumab or 35 administrations of study medication, or whichever occurs last;  
*Note: 24 months of study medication is calculated from the date of first dose. Subjects who stop pembrolizumab after 24 months may be eligible for up to one year of additional study treatment at the discretion of their treating physician, especially if their disease is clinically stable;*
- Administrative reasons
- Confirmed radiographic disease progression per RECIST criteria.
  - a. *Note: A subject may be granted an exception to continue on treatment with confirmed radiographic progression if clinically stable or clinically improved, please see Section 6.5*

The End of Treatment and Follow-up visit procedures are listed in Section 12 (Protocol Flow Chart) and Section 13. After the end of treatment, each subject will be followed for 30 days for adverse event monitoring (serious adverse events will be collected for 90 days after the end of treatment as described in Section 13.2.3.1). Subjects who discontinue for reasons other than progressive disease will have post-treatment follow-up for disease status until disease progression, initiating a non-study cancer treatment, withdrawing consent or becoming lost to follow-up. After documented disease progression each subject will be followed by telephone for overall survival until death, withdrawal of consent, or the end of the study, whichever occurs first.

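### The protocol gives conflicting rules on whether brain-only progression stops pembrolizumab, and on imaging versus telephone follow-up after progression, so late necrosis may be under-ascertained

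*Combined protocol and SAP*

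**What the plan says.** **Stopping pembrolizumab.** Section 11.1.11 begins "If a patient has new CNS lesions on the 6 weeks follow-up MRI", allows salvage SRS, whole brain or craniospinal radiation, and then states "The patient would still continue with anti-PD-1 treatments until progression of extra-cranial disease", with undue toxicity, about two years of treatment and physician discretion as the other limits. Section 11.1.9 likewise allows further brain radiation on trial for progressive disease.

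Section 2.1 has the drug "continued until at least 2 years or until disease progression per RECIST 1.1", with no site named. Section 6.5 lets a patient continue past a first progression at week 12 but stops the drug if the repeat scan shows further progression. Section 13.1.2.3 and the flow-chart footnote also stop at progression without limiting the site.

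Section 10.2 contains both rules. Under "A subject must be discontinued from the trial for any of the following reasons" it lists "Confirmed extra-cranial radiographic disease progression" and, as a separate item, "Confirmed radiographic disease progression per RECIST criteria". A note to the second item adds "A subject may be granted an exception to continue on treatment with confirmed radiographic progression if clinically stable or clinically improved" and refers to 6.5.

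**Follow-up after progression.** Section 10.2 states "After documented disease progression each subject will be followed by telephone for overall survival until death", and 13.1.2.4.1 likewise specifies a call every 12 weeks for survival status. Section 13.1.2.3 says that a patient stopped for progression is to have radiologic imaging every 12 weeks.

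**What depends on it.** Symptomatic radiation necrosis at 6 and 12 months is a secondary endpoint (3.2.2) that needs MRI evidence plus symptoms (3.2.3). Late toxicity feeds the choice of best arm (2.3). Section 14.3.1 reports late toxicity out of 12, or 6 without expansion. Section 14.3.4 uses cumulative incidence, with death as a competing risk and censoring at salvage whole brain radiation and/or last follow-up.

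**The concern.** Two patients with the same brain-only progression could be kept on or taken off the investigational drug according to which section the site follows. In a brain-metastasis trial this situation should be expected.

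The follow-up conflict affects any progressor. A survival call cannot establish necrosis, which needs an MRI and a neurological assessment. Necrosis found on a clinical scan can still be recorded, but whether such findings are collected systematically depends on the section used. A patient with no assessment stays in the 14.3.1 denominator and adds nothing to the numerator. In 14.3.4 the same patient is censored at last follow-up, possibly informatively, and the plan does not say whether that means the last brain assessment or the last call.

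**Working it through.** The plan gives no figure to reproduce on this point. The check is a comparison of texts, followed by a small illustration.

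**1. Does brain-only progression stop the drug?**

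| Source | Brain-only progression |
|---|---|
| 11.1.11 | Continue until extra-cranial progression |
| 10.2, extra-cranial bullet | Not a reason to stop |
| 10.2, RECIST bullet | Stop once confirmed, unless an exception is granted |
| 2.1 | Stop at RECIST 1.1 progression |
| 6.5 | Stop if the repeat scan shows progression |
| 13.1.2.3, flow-chart footnote | Stop at progression |

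Section 16.1 records brain MRI as a RECIST assessment, so brain lesions can trigger the RECIST bullet. If that bullet covers the brain, the extra-cranial bullet is redundant. If it does not, the text never says so. The exception does not settle this: it is discretionary, requires clinical stability, and refers to 6.5, which stops the drug on repeat progression.

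**2. What follow-up does a progressor get?** The explicit conflict is over imaging: 13.1.2.3 against 10.2 and 13.1.2.4.1. For toxicity it is less explicit. It rests on the flow chart, whose post-treatment column (as extracted) runs every 12 weeks for a year with Grade 3 CNS entries at 3, 6 and 12 months, and on the 3-monthly toxicity evaluation at follow-up visits in 11.1.10. Neither exempts progressors.

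**3. Could the safety windows cover the gap?** Section 10.2 monitors adverse events for 30 days after treatment and serious ones for 90. Take a patient with progression at week 12, confirmed 4 to 6 weeks later, and assume treatment ends at confirmation:

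- End of treatment: week 12 + 4 = 16 to 12 + 6 = 18.
- Adverse-event window closes: 16 + 30/7 = 20.3 to 18 + 30/7 = 22.3 weeks, before 6 months (26 weeks).
- Serious-event window closes: 16 + 90/7 = 28.9 to 18 + 90/7 = 30.9 weeks, before 12 months (52 weeks).

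So for such a patient the routine windows do not reach both necrosis time points. The 3-month DLT assessment falls before weeks 16 to 18, which is why the primary endpoint is little affected.

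**4. Effect of the denominator (illustration only).** Assume one necrosis case seen and m patients unassessed at 12 months. The documents give no value for m. The proportion among those assessed is 1/(n − m), with Clopper-Pearson 95% limits.

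| Arm size n | m | Fixed denominator | Among those assessed |
|---|---|---|---|
| 12 | 1 | 1/12 = 8.3% (0.2–38.5) | 1/11 = 9.1% (0.2–41.3) |
| 12 | 2 | 8.3% | 1/10 = 10.0% (0.3–44.5) |
| 12 | 4 | 8.3% | 1/8 = 12.5% (0.3–52.7) |
| 6 | 1 | 1/6 = 16.7% (0.4–64.1) | 1/5 = 20.0% (0.5–71.6) |
| 6 | 2 | 16.7% | 1/4 = 25.0% (0.6–80.6) |

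The fixed-denominator result does not change with m, and the intervals overlap heavily. The table shows why the number assessed should be reported. It does not estimate bias.

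**The case against.** **The specific rule governs.** Section 11.1.11 is the only section devoted to CNS progression. It states a default (continue) and says to contact the PI if in doubt. A reader might infer that the protocol has no default, or no brain-specific rule for progression first seen after the 6-week MRI. The text does not support either. Only the opening sentence of 11.1.11 is tied to that scan. Its continuation sentence, the extra-cranial bullet in 10.2 and the salvage allowance in 11.1.9 carry no time limit. What remains is that no section gives 11.1.11 precedence over a mandatory list that says otherwise.

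**Imaging continues anyway.** Brain MRI every 3 months is standard of care (2.1), and a survival call does not forbid it. If 11.1.11 is followed, brain-only progressors stay on treatment-phase visits, so lost data would mainly concern patients stopped for extra-cranial progression. This narrows the concern, but a scan done clinically is not the same as a result and a toxicity grade collected for the trial. The blood draw one year after stopping for progression (12.2) adds little, because it says nothing about imaging or toxicity.

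**The harm is unquantified.** A reader might infer from the 14- and 22-week progression-free survival in 4.2.1 that most of an arm would go unassessed. The documents do not support that. Those figures are for pembrolizumab alone, and 4.4.1 says the published melanoma trials excluded brain metastases. The closest counts by site, also in 4.4.1, are from 18 patients with melanoma brain metastases given pembrolizumab alone: 3 not evaluable because of extracerebral progression, and progression in 7 of 14 evaluable. Section 4.0.2 adds 82% one-year local control with SRS. None of these gives a rate for the combination. Late necrosis also cannot stop enrolment (2.3), and arm choice involves no formal test. This objection stands as to size, but not as to the conflict itself.

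**Conclusion.** Both conflicts are in the current text. On the drug, 11.1.11 and one bullet in 10.2 continue pembrolizumab through brain-only progression, while five other places stop it at progression at any site. On follow-up, the imaging conflict is explicit and the toxicity conflict is weaker.

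The consequence is conditional. If the telephone rule is followed, symptomatic necrosis at 6 and 12 months may be under-ascertained, mainly in patients stopped for progression. The fixed denominator would then in effect treat the unassessed as event-free; that is an inference, because the plan does not say how they count. The number of patients affected cannot be estimated from the documents. A reader might take this as undermining the primary safety result, but the 3-month DLT is little affected. The point justifies a clarifying amendment because it concerns drug management and a named safety endpoint that informs arm choice.

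**What to change.** **Drug rule.** In 10.2, limit the RECIST progression bullet to extra-cranial progression. Cross-refer 2.1, 6.5, 13.1.2.3 and the flow-chart footnote to 11.1.11, so that brain-only progression does not by itself stop pembrolizumab. Keep the toxicity and physician-discretion stops. Keep also the clinical conditions in 6.5 (no symptoms or signs of progression, no decline in performance status, no rapid progression at critical sites), applied as the sponsor judges fit for salvageable brain disease. Word the first sentence of 11.1.11 to cover any post-SRS MRI.

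**Follow-up.** Reconcile 10.2 and 13.1.2.4.1 with 13.1.2.3 by separating stopping drug from leaving the trial. Collect standard-of-care brain MRI results and CNS toxicity grades to 12 months from C1D1 regardless of progression, unless the patient dies or withdraws consent.

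**Analysis.** In 14.3.1, report the number assessed for necrosis at 6 and 12 months beside the fixed denominator. In 14.3.4, define last follow-up for necrosis as the last brain assessment, keep the existing censoring at salvage whole brain radiation, and report necrosis seen after it descriptively.

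**Cost.** Amendment wording and a small amount of extra data collection after progression. The MRI schedule is already standard of care, and 13.1.2.3 already asks for 12-weekly imaging after progression.
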